4.5. Region of Pooled Countries

The countries will be pooled to 2 regions as described below in [Table 1](#) for analysis purpose.

Table 1: Pooled Countries by Region

Region	Country
United States	United States
Other	Poland, Canada, Spain, Israel, Finland, Germany, Italy, The Netherlands

5. TRIAL POPULATION

5.1. General

The ITT analysis set will be used for all trial population summaries unless otherwise specified. Summaries will be presented by treatment group and for all participants unless otherwise noted.

For continuous variables, descriptive statistics (n, mean, SD, SE, median, minimum, and maximum) will be provided. For categorical variables, participant counts and percentages will be provided. Categories for missing data will be presented if necessary.

5.2. Participant Disposition

Participants screened, screening failures, and the reasons the participants were not randomized will be summarized only for the overall group using participant counts.

Participants randomized (ie, in the ITT set), participants randomized but not treated, participants in the safety analysis set, full analysis set and per-protocol analysis set, participants who complete the trial, and participants who withdraw from the trial will be summarized using descriptive statistics. Participants who withdraw from the trial will also be summarized using descriptive statistics by reason for withdrawal. The denominator for calculating the percentages will be the number of ITT population.

5.3. Demographics and Baseline Characteristics

The demographic data including date of birth (or year of birth), sex, country, ethnicity, and race will be collected at the screening after the participant signs informed consent. Participants' demographics and baseline characteristics including age, age in categories, sex, country, ethnicity and race, race by subgroups, region, body weight, body weight in categories, height, body mass index, years of migraine, migraine with aura, time since initial migraine diagnosis (years), protocol version, concomitant preventive medication use for migraine and any triptans/ergots during baseline will be summarized for ITT population. The demographic characteristics will be summarized for each of the analysis sets.

The baseline e-diary efficacy variables, baseline PedMIDAS scores and PedsQL scores will be summarized by treatment group for the ITT population.

5.4. Medical History

All medical history will be coded using the Medical Dictionary for Regulatory Activities (MedDRA) version 26.0 or higher. The incidence of medical history abnormalities will be summarized using descriptive statistics by system organ class (SOC) and preferred term (PT). Participants are counted only once in each PT and SOC category. Summaries will be presented by treatment group and for all participants.

5.5. Prior Therapy and Medication

Any prior therapy, medication, or procedure a participant has had before IMP administration will be recorded on the CRF. Trade name or INN, indication, and dosage will be recorded. The

sponsor will encode all therapy and medication according to the World Health Organization (WHO) drug dictionary (WHODrug).

The incidence of prior therapies and medications will be summarized using descriptive statistics by therapeutic class and PT. Participants are counted only once in each therapeutic class category, and only once in each PT category. Prior therapies and medications will include all medications taken and therapies administered before the 1st day of IMP administration.

The subset of prior medications will be summarized for the following categories.

- Medication from Appendix C for migraine/headache
- Medication from Appendix C for other reason than Migraine/Headache
- Migraine/headache prevention medication not from Appendix C
- NSAIDs for migraine/headache
- NSAIDs for other reason than migraine/headache
- Triptan for migraine/headache
- Triptan for other reason than migraine/headache
- Ergot for migraine/headache
- Ergot for other reason than migraine/headache
- Medication used for symptoms during migraine attack other than pain
- Other

5.6. *Electrocardiography*

Electrocardiogram findings by Investigator (normal, abnormal not clinically significant and abnormal clinically significant) and by Cardiologist (normal, abnormal) overall and at last visit will be summarized.

5.7. *Physical Examinations*

Physical examinations results will be listed. Participants with at least 1 abnormal finding (overall) and abnormal findings for each category will be summarized.

5.8. *Childbearing Potential and Methods of Contraception*

All participants must be of non-childbearing potential or be using highly effective contraception as defined in the protocol. Information related to childbearing potential will be collected and listed.

Methods of contraception will be collected and this data will be listed.

5.9. *Trial Protocol Violations*

Protocol deviations (PD) will be collected and reviewed by the trial team prior to database lock and will be provided in a data listing. Participants with at least 1 important protocol deviation will be summarized for each category using descriptive statistics.

6. EFFICACY ANALYSIS

6.1. General

The primary efficacy endpoint (and some secondary and exploratory efficacy endpoints) will be derived from headache variables collected daily using an electronic headache diary device.

On each day, the participant or parent/caregiver will be asked to record diary data for the previous 24-hour period. Participants or parents/caregivers who report headache on the previous day will answer questions about the headache (ie, the number of hours with headache, headache severity, presence of associated symptoms, and use of acute migraine medications).

If a participant or parent/caregiver fails to complete the diary for the preceding day, the participant will be prompted to enter the missed day's information the next time he/she accesses the electronic diary, provided no more than 48 hours have elapsed since the end of the missed day. If more than 48 hours have elapsed since completion of a diary day, the participant or parent/caregiver will not be allowed to enter diary information for that day, and it will be considered a missed day.

Rating of headache severity and headaches lasting ≥ 2 hours for each day will be completed in the electronic diary.

If headache is reported, then headache severity will be subjectively rated by the participant or parent/caregiver on an 11-point numerical rating scale, where 0 is no pain and 10 is the most severe pain. Each headache severity rating from the 11-point numerical rating scale will be mapped to mild (1 to 3), moderate (4 to 6), or severe (7 to 10) for endpoint analyses (McCaffery and Beebe 1989). Participants or parents/caregivers will also record whether photophobia, phonophobia, nausea, and vomiting are present, and they will record any migraine medications (name of drug, number of tablets/capsules, and the dose in milligrams per tablet/capsule) taken on each day.

In addition to the headache diary device, the following questionnaires will be used for the assessments of migraine impairment, quality of life and satisfaction of treatment etc. during the trial.

- migraine disability assessment, as measured by the PedMIDAS questionnaire ([Appendix C](#))
- quality of life, as measured by the PedsQL questionnaire ([Appendix D](#))
- [REDACTED] ([Appendix E](#))

The **monthly average number of days or hours** of efficacy variables (eg, migraine days, days of headache with at least moderate severity, days of headache with any severity, total hours of headache with any severity, total hours of headache with at least moderate severity, days of use of any acute headache medications, days with nausea or vomiting, days with photophobia and phonophobia etc.) **during the 12-week period** after the 1st dose of IMP will be derived and normalized to **28** days equivalent using the following formula.

$$\frac{\sum \text{Days or hours of efficacy variable over the 12 week period}}{\sum \text{Days with assessments recorded in the eDiary for the 12 week period}} \times 28 \quad (1)$$

The **monthly number of days or hours** of efficacy variables **during a 4-week period** after each dose will be derived and normalized to **28** days equivalent using the following formula, where monthly data separated by each visit of IMP dosing will be used.

$$\frac{\sum \text{Days or hours of efficacy variable during the 4 week period}}{\sum \text{Days with assessments recorded in the eDiary for the 4 week period}} \times 28 \quad (2)$$

The **baseline values** will be calculated using all data collected in the run-in period, ie,

$$\frac{\sum \text{Days or hours of efficacy variable during the run - in period}}{\sum \text{Days with assessments recorded in the eDiary for the run - in period}} \times 28 \quad (3)$$

The **percentage of reduction** in the monthly average number of an efficacy variable will be calculated as

$$\frac{\text{baseline value} - \text{postbaseline value}}{\text{baseline value}} \times 100\% \quad (4)$$

where the baseline value is calculated by formula (3) and the postbaseline value in the equation is calculated by formula (1) for the variables **during the 12-week period** or by formula (2) for the variables **during the 4-week period** after each dose for months 1, 2 and 3.

The FAS will be used for all efficacy analyses unless otherwise specified. Summaries will be presented by treatment group as randomized (test IMP or placebo IMP), unless otherwise noted. Descriptive statistics for all efficacy data will be presented by month or visit as appropriate and over 12-week period.

The primary and secondary endpoints analysis will be repeated for the per-protocol analysis set.

6.2. Primary Efficacy Endpoint and Analysis

A migraine day will be defined as a calendar day (00:00 to 23:59) where the participant reports either of the following:

- A calendar day (0:00 to 23:59) demonstrating at least 2 consecutive hours of a headache that is accompanied by ≥ 1 migraine symptom(s)
- A calendar day (0:00 to 23:59) demonstrating a headache of any duration that was treated with acute headache medications (NSAIDs, paracetamol or triptans and ergot compounds)

The derivation logic is presented in [Appendix B](#).

6.2.1. Primary Estimand

For the primary efficacy objective, the following estimand attributes will be employed:

- a. **Treatment:** monthly sc administration of fremanezumab or matching placebo.
- b. **Population:** male or female participants between the ages of 6 to 17 years (inclusive) with a clinical history of recurrent headache consistent with the diagnosis of migraine for at least 6 months before screening and a history of ≥ 15 headache days per month on average during the 3 months prior to screening.

- c. **Endpoint:** change from baseline in the monthly average number of migraine days during the 12-week period after the first dose of IMP.
- d. **Population-level summary:** difference between the fremanezumab group and the placebo group for the mean change from baseline in the monthly average number of migraine days during the 12-week period after the first dose of IMP.

The treatment policy strategy will be applied for any intercurrent events including concomitant medication and treatment noncompliance, meaning all observed participant data will be used for assessing the primary estimand regardless of any intercurrent events. The potential intercurrent events and the strategies used to handle them are listed in [Table 2](#)

Table 2: Intercurrent Event Strategies

Intercurrent Event	Strategy	Analysis
Concomitant medication noncompliance	Treatment policy	Measurements after intercurrent event will be included in analysis
Treatment noncompliance	Treatment policy	Measurements after intercurrent event will be included in analysis
All other events and protocol deviations	Treatment policy	Measurements after intercurrent event will be included in analysis

As described in [Section 4.3](#) and [Section 6.1](#), if a participant has ≥ 10 days of e-diary data after 1st dose of IMP, his/her monthly average number of days/hours of efficacy variables during the 12-week period will be prorated to 28 days. Participants who have <10 days of e-diary data will be excluded from the full analysis set.

6.2.2. Primary Analysis of the Primary Estimand

The hypothesis testing for the primary analysis is

$$H_o : \delta_1 = \delta_2 \quad vs \quad H_a : \delta_1 \neq \delta_2$$

where δ_1 and δ_2 are the parameters of mean change from baseline in the monthly average number of migraine days for the TEV-48125 treatment group and the placebo group respectively. The estimated difference of TEV-48125 dose vs. placebo will be tested following the pre-specified fixed sequence as specified in [Section 7](#).

An analysis of covariance (ANCOVA) method will be applied for the primary analysis. The model will include treatment, sex, puberty status, region (United States or Other ([Table 1](#))), weight category ($<45.0\text{kg}$ or $\geq 45\text{ kg}$) and baseline preventive migraine medication use (yes/no) as fixed effects and the baseline number of migraine days as a covariate. The stratification factors (as randomized) will be used in the model. The least squares (LS) means for the treatment groups, LS means and corresponding 95% confidence intervals for the treatment differences (TEV-48125 – placebo), and associated p-value will be provided.

A hierarchical procedure will be used to control Type 1 error rate, as described in [Section 7](#).

6.2.3. Sensitivity Analysis

6.2.3.1. MMRM Analysis

A mixed-effects repeated measures (MMRM) analysis model will be implemented to estimate the mean change from baseline in the monthly average number of migraine days for the overall 3 months treatment period and by each month to support the primary analysis.

Each participant's monthly number of migraine days *during the 4-week period* for month 1, month 2 and month 3 will be calculated by formula (2) in Section 6.1 based on the e-diary responses for that month. If a participant is early terminated or has intermittent missing days and has less than 10 days of e-diary entries for a month, that month's value will be considered as missing as described in Section 4.3.

The MMRM model will include baseline value, treatment, puberty status, sex, region, weight category (<45.0 kg or ≥ 45.0 kg), baseline preventive migraine medication use (yes/no), month and treatment-by-month interaction as fixed effects, and participant in the repeated statement as a random effect. The stratification factors (as randomized) will be used in the model. The unstructured covariance structure will be used for the repeated observations within a participant. If the model does not converge, then simpler covariance structures with fewer parameters will be used in the following order (stopping at the first converging structure); heterogeneous Toeplitz, Toeplitz, or compound symmetry with a robust sandwich estimator (Liang and Zeger, 1986). For a model based estimator of the covariance (ie, unstructured, heterogeneous Toeplitz, or Toeplitz) for making inferences between treatment groups, especially at a particular visit, the Kenward-Roger degrees of freedom will be employed (Kenward and Roger, 1997).

LS means for the treatment groups, LS means for the treatment differences (TEV48125-48125 - placebo), and corresponding 95% confidence intervals and associated p-values will be calculated by month and for the overall treatment period.

The LS means \pm SE of monthly change from baseline values estimated by MMRM will be plotted by month for each treatment group.

A supplementary analysis using the ITT population will also be carried out for the primary efficacy endpoint.

A further supplementary analysis will be performed by week for the first month after baseline to support the primary analysis. The change from baseline (run-in period) in the number of migraine days *during the 4-week period* after the 1st dose of IMP will be derived similar to the primary endpoint using only the 1st month diary data.

6.2.3.2. Analysis with Multiple Imputation Method

Multiple imputation (MI) method will be applied to impute the monthly missing data assuming a missing not at random (MNAR) mechanism. The data will be processed by the following steps.

If a participant has partial e-diary data for a month, ie, <10 days of data, that month's value will be considered missing before the MI procedure.

For the participants in the active treatment groups who are early terminated with reasons of adverse event or lack of efficacy, they will be assigned to placebo group so their missing values will be imputed using data from the placebo treated participants.

Run SAS PROC MI procedure to create 100 complete datasets.

Within each imputed data set, for a participant who has partial, say X days (X<28), e-diary data in a month, the monthly value will be replaced by

$$\Sigma(\text{observed migraine days}) + (28 - X) * \text{imputed value}/28$$

The monthly average number of migraine days **during the 12-week period** after the 1st dose of IMP will be the average of month 1, month 2 and month 3 values.

SAS PROC MIANALYZE procedure will be used to find the average number of migraine days during the 12-week period for both treatment groups. It will find the mean and standard errors of both the average number of migraine days and the change from baseline over the 100 datasets.

Each dataset will be analyzed using the same ANCOVA model as described in Section [6.2.2](#). The LS means and standard errors from each analysis will be output to a SAS data set. SAS PROC MIANALYZE procedure will be used to generate the final LS means (\pm SE) for the treatment groups and the treatment differences (TEV-48125 – placebo) as well as p-values associated with treatment differences. The 95% confidence intervals for the treatment differences will also be constructed.

The output dataset will contain the estimate of the mean difference and the standard error of the estimate from each of the 100 datasets. SAS procedure, PROC MIANALYZE, will be used to generate an overall p-value and 95% CI for the treatment difference.

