01	12 October 2023	Section 5.3: Text referring to analysis of baseline factors removed.	No longer required.
01	12 October 2023	Section 5.5: WHO Drug changed to WHODrug.	Correction.
01	12 October 2023	Section 6.1: Text referring to weekly values removed	Sensitivity analyses relating to weekly values removed.
01	12 October 2023	Section 6.2: Inclusion of NSAIDs and paracetamol and removal of the word migraine from the list of specific medications.	Correction.
01	12 October 2023	Section 6.2.2: Removal of the word 'each' when referring to the estimated difference of TEV-48125 dose vs. placebo.	Correction.
01	12 October 2023	Section 6.2.2: Addition of baseline weight group as a fixed effect to the ANCOVA model and minor amendments to the example SAS code.	Minor corrections to SAS code and the addition of baseline weight group in order that the effects may be controlled for.
01	12 October 2023	Section 6.2.2: Addition of stratification factor text.	Clarification that the stratification factors (as randomized) will be used in this analysis model.

Version number	Date	Summary of changes	Reason for amendment
01	12 October 2023	Section 6.2.2: Addition of text regarding the assessment of the residuals from the ANCOVA model.	Clarification that in addition to ANCOVA, the Wilcoxon rank-sum test will be conducted and the most appropriate analysis selected once the normality of the residuals from the ANCOVA model have been assessed.
01	12 October 2023	Section 6.2.3.1: Addition of stratification factor text.	Clarification that the stratification factors (as randomized) will be used in this analysis model.
01	12 October 2023	Section 6.2.3.1: Addition of baseline weight group as a fixed effect to the MMRM model and minor amendments to the example SAS code.	Minor corrections to code and the addition of baseline weight group in order the effects may be controlled for.
01	12 October 2023	Section 6.2.3.1: TV48125 changed to TEV-48125.	Correction.
01	12 October 2023	Section 6.2.3.2: Added text to clarify that the Multiple Imputation method will assume a missing not at random mechanism.	Not previously included.
01	12 October 2023	Section 6.2.3.2: (X<10) text changed to (X<28).	Correction.
01	12 October 2023	Section 6.2.3.2: SAS PROC MI procedure text changed to specify that 100 complete datasets rather than 10 complete datasets will be produced.	Consistency with other studies.

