4.3. Handling Withdrawals and Missing Data

If a participant has ≥ 10 days of the e-diary data after 1st dose of IMP, his/her monthly average number of days/hours of efficacy variables ***during the 12-week period*** or monthly number of days/hours of efficacy variables ***during the 4-week period*** will be prorated to **28** days.

Participants who have <10 days/hours of diary data will be excluded from the full analysis set.

Multiple imputation (MI) method will be applied on the primary variable as sensitivity analyses. The methods will be described in detail in Section [6.2.3](#).

A participant's monthly number of days/hours of efficacy variables ***during the 4-week period*** after each dose of IMP will be calculated for months 1, 2, and 3. If a participant has missing diary days in a month, the following method will be used to handle the missing data.

- If the participant has 10 or more days of e-diary data for a month, the monthly number of days/hours of efficacy variables will be prorated to **28** days for that month.
- If the participant has less than 10 days of e-diary data for a month, the monthly number of days/hours of efficacy variables will be considered as missing.

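### SAP 6.2.3.2 defines a partial month in two ways, so active-arm withdrawals for adverse event or lack of efficacy keep their on-treatment rate in a withdrawal month with 10 to 27 diary days

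*SAP*

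**What the plan says.** SAP 6.2.3.2 imputes monthly values of migraine days "assuming a missing not at random (MNAR) mechanism". The steps, in order:

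1. A month is set to missing before PROC MI under this condition: "If a participant has partial e-diary data for a month, ie, <10 days of data".
2. Active-arm participants "who are early terminated with reasons of adverse event or lack of efficacy" are handled so that "they will be assigned to placebo group so their missing values will be imputed using data from the placebo treated participants".
3. PROC MI creates 100 completed datasets.
4. Within each dataset, "for a participant who has partial, say X days (X<28), e-diary data in a month, the monthly value will be replaced by" the sum of observed migraine days plus (28 − X) × imputed value/28.
5. The 12-week value is the average of months 1, 2 and 3. Each dataset is analysed with the primary ANCOVA and the results are combined.

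SAP 4.3 governs the monthly values that enter step 1: "If the participant has 10 or more days of e-diary data for a month, the monthly number of days/hours of efficacy variables will be prorated". The base for this proration is a 28-day month. Below 10 days the monthly value is missing.

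The SAP amendment history shows that version 01 moved the bound in the step 4 formula from 10 to 28 days. Step 1 still uses 10.

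**The concern.** Step 1 treats a month as partial below 10 diary days, and step 4 treats it as partial below 28. Months with 10 to 27 days fall between the two. They carry a prorated value, so PROC MI has nothing to impute, yet step 4 calls for an imputed value.

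This matters for the participants named in step 2. Diary entry ends at the early withdrawal visit (protocol Table 1, diary footnote), so the days after withdrawal are unobserved. Someone who stops after 10 or more days of a month has the rest of that month filled at their own pre-withdrawal rate, which is the same assumption that the primary proration makes.

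For the primary endpoint this is the only planned analysis stated as MNAR. The MMRM (SAP 6.2.3.1) also prorates months with 10 or more days, and the repeat ANCOVA (SAP 6.2.3.3) changes only the stratification values. Two programmers could also follow the section differently and both claim to comply.

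**Working it through.** **The plan's own figures.** The imputation section states no numerical result. The sample size in SAP 2.4 supplies the scale: difference 1.7 days, SD 4.92, 133 evaluable per arm, two-sided 0.05.

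- Power: 0.804 (normal approximation) or 0.802 (noncentral t), against a stated minimum of 80%.
- Randomized: 266/(1 − 0.04) = 277.1, rounded up to 278, as stated.
- Standard error of the treatment difference: 4.92 × √(2/133) = 0.60 days.

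SAP 2.4 gives the 1.7 and 4.92 for headache days of at least moderate severity. Using them for migraine days is an assumption.

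**What the formula returns for X = 10 to 27.** Let *obs* be the migraine days recorded in X diary days. The only monthly value in a PROC MI output dataset is the retained prorated one, obs × 28/X. Substituting it in step 4:

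obs + (28 − X) × (obs × 28/X)/28 = obs + (28 − X) × obs/X = obs × 28/X.

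This is the prorated value again, whatever X is.

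**Example (assumed counts).** X = 10, obs = 3.

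- Prorated value: 3 × 28/10 = 8.4.
- Formula as written: 3 + 18 × 8.4/28 = 8.4.
- Formula with a placebo-based value 1.7 days higher (10.1): 3 + 18 × 10.1/28 = 9.49.
- Difference: 1.09 days for the month, and 1.09/3 = 0.36 for the 12-week average.

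**Size per participant.** If the full 1.7-day effect is assumed lost after withdrawal, the shift in the 12-week average is (28 − X) × 1.7/(28 × 3):

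- X = 10: 18 × 1.7/84 = 0.36 days
- X = 18: 10 × 1.7/84 = 0.20 days
- X = 27: 1 × 1.7/84 = 0.02 days

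**Size for the active-arm mean.** This assumes that every discontinuation is for adverse event or lack of efficacy.

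- 4% (SAP 2.4), all at X = 10: 0.04 × 0.364 = 0.015 days, about 0.02 standard errors.
- 4%, withdrawal spread evenly over days 10 to 83: about 0.006 days.
- 10% (assumed): at most 0.036 days, and 0.014 with even spread.

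**How much of the follow-up is affected.** Assume withdrawal is uniform over days 10 to 83 of the 84-day period.

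- Post-withdrawal days in total: 74 + 73 + … + 1 = 2,775.
- Those in months with 10 to 27 observed days: 3 × (18 + 17 + … + 1) = 3 × 171 = 513.
- Share not imputed from placebo: 513/2,775 = 18%.
- Withdrawal days for which nothing at all is imputed from placebo: the 18 in month 3 with 10 to 27 days observed, 18/74 = 24%.

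**The case against.** A reader might infer that every withdrawer with 10 to 27 diary days escapes the MNAR assumption, and that the analysis agrees with the primary result by construction. The documents do not support this. The placebo rule covers only active-arm terminations for adverse event or lack of efficacy, so other withdrawers were never under it. Among those it covers, only the truncated month is affected. Later empty months are still imputed from placebo, so full escape needs a month-3 withdrawal with 10 or more days.

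Intent can also be argued. The change of the bound to 28 is logged as a correction, which suggests that imputed values were meant for all incomplete months. But step 1 and SAP 4.3 were not changed to match, and no other text says what the imputed value is for 10 to 27 days. Example code has been removed from the SAP, so the documents do not show what was programmed. They support only what follows from running the written steps.

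Nor is the on-treatment rate implausible within that month. Month windows run from dose to dose (SAP 4.4), and the protocol equates 150 days with five half-lives, about 30 days each. A participant who stops 10 to 27 days after a dose still has substantial exposure. That could justify a different rule, but it is not the assumption that SAP 6.2.3.2 states.

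Finally, the 50% responder endpoint counts early discontinuation as non-response (SAP 6.3.1.1), so withdrawal is penalised elsewhere in the testing hierarchy. That is correct, but it does not test the primary endpoint.

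**Conclusion.** The point holds as a specification defect in one sensitivity analysis. Run as written, the steps leave months with 10 to 27 diary days at the participant's own rate. For active-arm withdrawals for adverse event or lack of efficacy, this contradicts the stated placebo-based imputation.

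The consequence is small: at most about 0.015 days on the active-arm mean at 4% discontinuation, against a standard error of 0.60. That bound assumes loss of the full 1.7-day effect, all discontinuations of the named types, and all of them at the least favourable day. A claim that robustness is materially overstated would go beyond these figures. The primary ANCOVA and the type 1 error control are untouched. The correction is still worth making, because the rule does not do what it says and the change is a single condition.

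**What to change.** Use one definition of a partial month in SAP 6.2.3.2.

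- For active-arm participants terminated for adverse event or lack of efficacy, set the month truncated by withdrawal to missing before PROC MI, even if it has 10 to 27 diary days.
- Then apply the stated formula, so that observed days are kept and only unobserved days take the placebo-based value.
- Limit the formula to months set to missing. Leave intermittent gaps, and all other months with 10 or more days, prorated as in SAP 4.3. Visit windows of ±3 days mean that a fully completed month can have fewer than 28 days, so a bare X<28 condition is too wide.

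The cost is a change of wording and one data-step condition. The sensitivity estimate may become slightly less favourable. The truncated month's prorated value is also lost as a predictor in the imputation model. For a month-1 withdrawal, that is the only on-treatment monthly value available to inform months 2 and 3.

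SAP 2.5.2 requires amendments before database lock, and the May 2025 note to file says that the trial analysis was conducted. If this analysis has already been run, the CSR should state which rule was programmed for months with 10 to 27 days and report a rerun under the consistent rule as post hoc.
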